## **STUDY DESIGN**:

Prospective research and development study

## **ELIGIBILITY CRITERIA**

#### Inclusion criteria:

#### Ground truth:

- Normal or corrected to normal vision or with strabismus.

Clinical study:

- Strabismus
- Ability to keep looking at the target for 30-60 seconds
- Able to report location of the target
- Uncorrected visual acuity of 20/30 or better

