# AIM

## AIM 1:

Develop and test key functionality of the strabismus app by comparing measurements with successive versions of the prototype app to known angles of eye deviation (non-strabismic volunteers will gaze at off axis targets of known eccentricity).

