The app offers various operating modes through which the eve deviation can either be measured monocularly or binocularly. Additionally, the app also allows dissociated measurement, for example to measure intermittent strabismus condition or phoria, where the deviation between the eyes is not manifest. In clinic, measurement under dissociated conditions is done by performing either cover-uncover or alternate- cover tests with prisms (CTPN). One key feature of the app is the ability to measure eye deviations under dissociated conditions without the need for prism neutralization. In this operational mode, the examiner presses a button to record a video, while the patient fixates on a target binocularly. The patient's binocular fusion is broken in the traditional manner by either cover-uncover (of one eye) or alternate cover (involving both eyes). The examiner ultimately uncovers one eye, and the app records this entire event as a video sequence (Fig. 2). The user is prompted with audio tones to assist in the timing of the cover- uncover. The video frame just after uncovering an eye can be selected for processing the maximum dissociated eye deviation. Due to the high framerate of video capture (30 Hz), we can measure the deviation before a recovery vergence eye movement can be initiated. Figure 2b shows an example of the eye movement trace obtained when performing the alternate cover test, with a smartphone recording the video of this event.

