#### **Ground truth study:**

The subjects will sequentially fixate on the targets of known eccentricity placed on the rear surface of the smartphone along the horizontal direction with their head stabilized in a chin forehead rest (Fig. 3). The app does not need to be used in this manner in actual practice; however, for the purpose of establishing the true deviation values for the fixation targets, such a controlled setup was necessary. The test setup covered an angular range of  $\pm 13$  degree (approximately  $\pm 23D$  with respect to a central fixation corresponding to camera lens).

Figure 3. Experimental setup to measure the accuracy of the app in Study 1. Subjects without strabismus fixated on 13 targets on the rear side of a smartphone placed at a distance of 30 cm with their head resting on a chin–head rest. Twelve of the 13 fixation targets were a black cross on a white background. The center target was the smartphone camera. With the known distances, true eye deviation magnitudes with respect to the central fixation point were computed (angular range covered by the fixation targets was 6138 or 623D) and compared to measurements with the app.

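### The ground-truth inclusion line admits people with strabismus, contrary to Aim 1 and the Figure 3 caption, and the plan does not say which eye is measured or how it views the target

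*Protocol*

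**What the plan says.** The Protocol describes the ground-truth sample in three places.

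- Eligibility Criteria, Inclusion criteria, Ground truth: "Normal or corrected to normal vision or with strabismus".
- Aim 1: "non-strabismic volunteers will gaze at off axis targets of known eccentricity".
- Ground truth study, Figure 3 caption: "Subjects without strabismus fixated on 13 targets on the rear side of a smartphone".

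The Hypotheses section also equates ground truth with simulated strabismus. The Exclusion criteria concern only holding fixation and reporting the target's location, so they do not remove anyone for strabismus.

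The reference value comes from the layout of the targets, not from a measurement of the eye: "With the known distances, true eye deviation magnitudes with respect to the central fixation point were computed". The procedure is that "The subjects will sequentially fixate on the targets of known eccentricity placed on the rear surface of the smartphone along the horizontal direction", with the head stabilized. No eye is named and no occlusion is mentioned. Study Procedures says that the app has both monocular and binocular modes, so the mode used here cannot be inferred.

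For Aim 1, the SAP regresses the app measurement on the known target angle for each subject. The slope is the HR and the intercept is angle kappa. It then compares absolute gaze angles from the app with the target angles, using for each subject the average HR of the others. It has no separate handling for strabismic subjects.

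**The concern.** The three descriptions of the sample cannot all govern enrolment. The inclusion line is the operative rule, and it is the one that does not suit the method. A target's angle is the true gaze angle only for an eye pointing at that target. In manifest strabismus, one eye fixates and the other is off target by an amount that the target geometry does not know.

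If the non-fixating eye is the one analysed, the regression treats the participant's own deviation as part of kappa, and the accuracy analysis treats it as app error. Agreement with ground truth is one of the two comparisons in the primary outcome, and the mean difference from simulated strabismus is a secondary outcome. A reader should therefore be able to tell who formed this sample and which eye supplied the data.

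**Working it through.** **Inputs.** Target half-range 13 degrees, given as about 23 PD (Protocol, Ground truth study). App resolution 1.6 degrees, given as 2.8 PD (Protocol, Background). Target range of strabismus 1 to 30 PD (Protocol, Hypotheses). Per-subject linear fit over 13 fixation points (SAP, Aim 1). The documents give no distribution of deviations and no number or share of strabismic subjects in this part.

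**Step 1: reproduce the plan's own conversions.** With PD = 100 × tan(angle):
- 100 × tan(13°) = 23.09, stated as about 23.
- 100 × tan(1.6°) = 2.79, stated as 2.8.

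Both agree, so the inverse, angle = atan(PD/100), is used below.

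**Step 2: constant deviation, deviating eye measured.** If the target is at angle t and the measured eye is off by a constant d, true gaze is t + d. On the degree scale, regressing t + d on t gives slope 1 and intercept d. Even spacing of the 13 targets from -13 to +13 degrees was assumed in the calculation, but this result does not depend on it.

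| Deviation (PD) | Shift in kappa and absolute gaze angle (degrees) | Multiple of 1.6 degrees | Slope | Error relative to own central fixation |
|---|---|---|---|---|
| 1 | 0.57 | 0.4 | 1.00 | 0 |
| 5 | 2.86 | 1.8 | 1.00 | 0 |
| 10 | 5.71 | 3.6 | 1.00 | 0 |
| 20 | 11.31 | 7.1 | 1.00 | 0 |
| 30 | 16.70 | 10.4 | 1.00 | 0 |

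The shift passes the app's stated resolution at about 2.8 PD (step 1). At 30 PD it exceeds the 13-degree half-range. The shift in absolute gaze angle would vanish if each subject's own intercept were subtracted first; the SAP does not say whether this is done.

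**Step 3: deviation that varies with gaze.** Assume a 10% change, so that gaze = 1.1t + d. The slope becomes 1.10. The mean absolute error relative to central fixation is 0.1 × mean|t| = 0.1 × 7.0 = 0.7 degrees. The HR is now biased, and the average HR of the other subjects carries part of that bias to everyone else.

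**Step 4: fixating eye measured.** Gaze = t, so slope is 1.00, intercept shift 0 and error 0.

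**Step 5: group mean.** Assume that 10% to 50% of subjects contribute a deviating eye of 10 PD, all in the same direction. The mean bias is then 0.10 × 5.71 = 0.57 to 0.50 × 5.71 = 2.86 degrees. Deviations in opposite directions would partly cancel in the mean and appear as extra spread.

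**The case against.** The strongest reply is that this is a drafting slip without consequence. The Figure 3 caption reports, in the past tense, that subjects without strabismus were tested. The SAP is also in the past tense and says it was produced when the data were published. Nothing in either document shows a strabismic participant in the ground-truth set. This stands: the documents show a risk created by the rule as written, and they do not show realised bias.

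A reader might also infer that the method requires both eyes to be on the target, so that any strabismic participant is invalid. The documents do not say so. Kappa belongs to a single eye, the app can measure monocularly, and the fixating eye of a strabismic participant has a perfectly good reference value. Study Procedures also recognises intermittent strabismus and phoria, in which the deviation need not be manifest. The requirement is that the measured eye be on target.

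A reader might further infer that the error would undermine the rest of the study. That is not supported either. The Aim 2 comparisons are with the cover test with prism neutralization (SAP) and the Modified Thorington test (Protocol, Clinical study), and neither uses Aim 1 target angles or kappa. The app's conversion factor is taken from the range of previously reported HR values. The one link is that Objective 2 uses the prototype optimized under Objective 1, and nothing shows that an offset in kappa would change which algorithm is chosen.

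What survives is the contradiction about the sample, together with silence on the measured eye and viewing condition.

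**Conclusion.** The point holds in a limited form. The inclusion line contradicts Aim 1 and the Figure 3 caption, and nothing in the Exclusion criteria or the SAP prevents a deviating eye from being scored against the target angle.

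The exposure is confined to kappa and the absolute gaze angle, at 0.57 to 16.7 degrees per affected subject over 1 to 30 PD. The 11.3-degree figure rests on an assumed deviation of 20 PD. The bias requires three things together: manifest strabismus, the other eye left to fixate, and analysis of the deviating eye. With a constant deviation, the HR and values relative to the subject's own central fixation are unbiased. They are biased only if the deviation varies with gaze, and the 10% used to illustrate that is an assumption, as are the shares in the group-mean example.

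It should be corrected because the rule defines a reference sample and the correction is nearly free. It is not evidence that the reported ground-truth results are wrong.

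**What to change.** Reconcile the ground-truth inclusion line, Aim 1 and the Figure 3 caption. The simplest change is to delete the strabismus clause from the ground-truth inclusion line, leaving normal or corrected-to-normal vision.

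If strabismic participants are to be kept, state the viewing condition, analyse only the fixating eye, and report these participants separately from the kappa and absolute gaze angle results.

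In either case, state which eye is measured, whether each subject's own kappa is subtracted before absolute gaze angles are compared, and whether any strabismic participant was in the ground-truth set. If any were, repeat the Aim 1 regressions and the average-HR analysis without them.

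The cost is a one-line protocol correction and a few sentences in the SAP, with no added participants or visits. The re-analysis is needed only if strabismic participants were included.

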## **Exclusion criteria:**

- Inability to keep looking at the target for 30-60 seconds
- Inability to report location of the target

## **STUDY OUTCOMES**

## Primary outcome:

The primary outcome is a comparison between the app and the ground truth and between the app and clinical tests.

## Secondary outcome:

1) Accuracy of the app quantified by calculating the mean difference between the app and simulated or measured strabismus.

2) Test-retest repeatability

3) Robustness measure: calculation of the percentage of capture failures (capture failures/ total number of attempted image captures)

4) Analysis of the effect of different factors (i.e. age, iris color, refractive error) on the accuracy.

5) Success rate of tele-strabismus consult and perceived value (captured in a perceived value survey).

## **STUDY PROCEDURES**

Using a conventional smartphone with a high resolution rear camera and flash (for example, Samsung Galaxy S4 and above; Samsung, Seoul, South Korea, and iPhone 5 and above; Apple, Cupertino, CA), the EyeTurn app automatically detects the difference in corneal reflection position relative to the eye center (based on fitting a curve to the limbus boundary) to calculate ocular misalignment, and provide an objective measure of eye deviation from the captured image

of the patient's eyes (Fig 1). The captured images are processed entirely within the smartphone using custom image processing algorithms, and the eye deviation measurements are displayed on the screen usually within a couple of seconds. We use iris center (center of the eye, or the center defined by the limbus curve) instead of pupil center as the reference for computing the corneal reflection decentration, as it has been reported to be a more robust reference for measuring ocular alignment, especially when computing binocular differences (Barry JC, Backes A 1997). Also, for darker iris colors, the limbus boundary is better-delineated than the pupil boundary in visible spectrum images captured by a typical smartphone camera. The corneal reflection decentration distance is converted to prism diopters (D) using an HR in the range of previously reported values (Jagini, 2014).

Figure: 1 The EyeTurn app for measurement of eye deviations. (Left) Features detected by the app via automatic image processing: limbus boundary denoted by a green circle, its center denoted by a green cross, and the corneal reflection due to the flash denoted by a red dot. The distance between the eye center and corneal reflection, shown as 'd', is compared between the two eyes to detect eye deviation. (Right) To measure the eye alignment using a single picture, the phone is held 30 cm from the eyes of the subject and a picture is taken as the subject fixates binocularly. This mode of operation is well suited for measuring or screening for manifest eye deviation. Permission to publish photograph was obtained via a signed consent to publish document.

The app offers various operating modes through which the eve deviation can either be measured monocularly or binocularly. Additionally, the app also allows dissociated measurement, for example to measure intermittent strabismus condition or phoria, where the deviation between the eyes is not manifest. In clinic, measurement under dissociated conditions is done by performing either cover-uncover or alternate- cover tests with prisms (CTPN). One key feature of the app is the ability to measure eye deviations under dissociated conditions without the need for prism neutralization. In this operational mode, the examiner presses a button to record a video, while the patient fixates on a target binocularly. The patient's binocular fusion is broken in the traditional manner by either cover-uncover (of one eye) or alternate cover (involving both eyes). The examiner ultimately uncovers one eye, and the app records this entire event as a video sequence (Fig. 2). The user is prompted with audio tones to assist in the timing of the cover- uncover. The video frame just after uncovering an eye can be selected for processing the maximum dissociated eye deviation. Due to the high framerate of video capture (30 Hz), we can measure the deviation before a recovery vergence eye movement can be initiated. Figure 2b shows an example of the eye movement trace obtained when performing the alternate cover test, with a smartphone recording the video of this event.

Figure 2. Cover testing mode for dissociated measurements using the app. (Top row) Alternating cover–uncover test using the video-based cover test mode. This novel operational mode can be used for dissociated measurements. The examiner alternately covers the eyes (first two images on top row). The frame with both eyes uncovered (third image on the top row) is selected for automatic processing by the app for measurement of the eye deviation. (Bottom row) Eye movement trace after offline processing of the video of the alternate cover test shows the movements of the eyes after the cover is removed. Negative values show temporal deviation (outward), whereas positive values show nasal deviation (inward). There is a brief duration after removing the cover during which the deviation can be measured (highlighted by the oval gray zone). It should be noted that the eye movement trace in this figure was generated by processing the video recorded by the smartphone on a desktop computer using the same image processing software used in the app, but may be included as part of the app in the future. Permission to publish photograph was obtained via a signed consent to publish document.

#### **Ground truth study:**

The subjects will sequentially fixate on the targets of known eccentricity placed on the rear surface of the smartphone along the horizontal direction with their head stabilized in a chin forehead rest (Fig. 3). The app does not need to be used in this manner in actual practice; however, for the purpose of establishing the true deviation values for the fixation targets, such a controlled setup was necessary. The test setup covered an angular range of  $\pm 13$  degree (approximately  $\pm 23D$  with respect to a central fixation corresponding to camera lens).

Figure 3. Experimental setup to measure the accuracy of the app in Study 1. Subjects without strabismus fixated on 13 targets on the rear side of a smartphone placed at a distance of 30 cm with their head resting on a chin–head rest. Twelve of the 13 fixation targets were a black cross on a white background. The center target was the smartphone camera. With the known distances, true eye deviation magnitudes with respect to the central fixation point were computed (angular range covered by the fixation targets was 6138 or 623D) and compared to measurements with the app.

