## **HYPOTHESES**:

For strabismus ranging from 1 to 30 prism diopters (target range), the optimized version of the app will provide measurements which are not significantly different from the ground truth (simulated strabismus) or clinical tests of eye alignment.

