Statistical Analysis Plan

Produced during publication of data

[name], [name], [name], [name], [name]; Development and Preliminary Evaluation of a Smartphone App for Measuring Eye Alignment. *Trans. Vis. Sci. Tech.* 2019;8(1):19.

August 1, 2019

Aim 1: Simulated Strabismus

The Hirschberg ratio (HR) for each subject was determined using data from all 13 fixation points by plotting the app measurement against the known angular deviation for each fixation point, and determining best fit of this scatter plot using linear regression. The slope of this function represents the individual's HR and the *y*-intercept is the individual's angle κ (the angle between the visual and optical axes, represented as κ).^{18,19} We measured the within-subject test–retest repeatability of the app in estimating the HR and κ using a Bland-Altman²⁰ plot to compute 95% confidence interval (CI) of the difference between two trials. Furthermore, we tested the accuracy of using a population average value of the HR by comparing the absolute gaze angles estimated by the app measurements and the true deviation of the fixation targets (via regression analysis using MATLAB; Mathworks, Natick, MA). The HR used for a subject was the average HR of the rest of the subjects.

Aim 2: Strabismus

Linear regression analysis was used to compare the app measurements of strabismus angle with cover test with prism neutralization CTPN measurements. Since the CTPN measurements were done at near fixation to facilitate direct comparison with the app measurements, corrections were made to the recorded CTPN values during data processing to account for the finite distance between the prism and center of rotation of the eye.²² We arrived at a value of the distance between prism and center of rotation of eye by assuming a population average value of 24 mm for axial length²³ and a back vertex distance of 10 mm.

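### The ground-truth study measures per-eye gaze angle out to about 23 PD, but the protocol presents it as simulated-strabismus accuracy over 1 to 30 PD, a between-eye quantity

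*Protocol*

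**What the plan says.** **What the app reports.** Protocol, Study Procedures (Figure 1 legend): the distance from eye centre to corneal reflection "is compared between the two eyes to detect eye deviation". For manifest deviation this comes from one photograph: "a picture is taken as the subject fixates binocularly".

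**What the ground-truth study measures.** Protocol, Aim 1: "non-strabismic volunteers will gaze at off axis targets of known eccentricity". The Figure 3 legend adds "Subjects without strabismus fixated on 13 targets on the rear side of a smartphone placed at a distance of 30 cm", and the reference value is defined there: "true eye deviation magnitudes with respect to the central fixation point were computed". The running text gives the range as ±13 degrees, about ±23 PD.

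**How it is analysed.** SAP, Aim 1: each subject's app readings are regressed on the target angles. The slope is taken as the HR and the intercept as angle kappa. Accuracy with a leave-one-out average HR is then assessed by "comparing the absolute gaze angles estimated by the app measurements and the true deviation of the fixation targets".

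**What is claimed from it.** Protocol, Hypotheses: "For strabismus ranging from 1 to 30 prism diopters (target range"), the app should not differ significantly from ground truth, which is equated with simulated strabismus, or from clinical tests. Secondary outcome 1 defines accuracy as the mean difference between the app and simulated or measured strabismus. The SAP also heads its Aim 1 section with the term simulated strabismus.

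**The concern.** A volunteer with aligned eyes who looks 13 degrees to the side has turned both eyes by nearly the same amount and has no strabismus. The known angle in Aim 1 is a gaze eccentricity. The quantity the app offers clinicians is the difference between the eyes. An accuracy figure for the first does not automatically carry over to the second, because a between-eye reading also contains any difference in kappa or HR between the two eyes and the reading error of the second eye.

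Aim 1 is the only part of the programme with a geometrically known truth, so its result is likely to be quoted as the app's accuracy for strabismus. It would also be quoted for a range whose upper end, 23 to 30 PD, has no targets.

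**Working it through.** **1. Stated range.** With PD = 100 × tan(angle), 13 degrees gives 23.09 PD, which matches the stated 23. The Background's 1.6 degrees gives 2.79 PD, which matches the stated 2.8. The top of the target range, 30 PD, is atan(0.30) = 16.7 degrees. The ground-truth targets stop at 13.

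**2. Can the Aim 1 reading be a between-eye reading?** Inputs: distance 300 mm and extreme target at 13 degrees (protocol), so the target offset is 300 × tan(13°) = 69.26 mm. Interpupillary distance (IPD) is not given, so 50 to 70 mm is assumed. With eyes at ±h (h = IPD/2) and a target at offset x, the right eye's rotation from fixating the camera is atan((x − h)/300) − atan(−h/300). For the left eye, replace h by −h.

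Example, IPD 60 mm:
- one eye: atan(39.26/300) + atan(30/300) = 7.46 + 5.71 = 13.17 degrees
- other eye: atan(99.26/300) − atan(30/300) = 18.31 − 5.71 = 12.60 degrees
- between-eye difference: 0.57 degree

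| Assumed IPD | One eye | Other eye | Difference |
|---|---|---|---|
| 50 mm | 13.16° | 12.68° | 0.48° (0.83 PD) |
| 60 mm | 13.17° | 12.60° | 0.57° (0.99 PD) |
| 70 mm | 13.17° | 12.51° | 0.66° (1.15 PD) |

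The difference is the same at +13 and −13 degrees, so its linear slope on target angle is zero. A single eye's slope is 0.987 to 0.993 (equally spaced targets assumed). A between-eye reading would thus give a slope near zero and an intercept near the between-eye kappa difference. The SAP's reading of slope as HR and intercept as kappa works only if each eye is analysed by itself. The documents never say so outright, but the model and the geometry leave little alternative.

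**3. Coverage.** As a between-eye quantity, Aim 1 exercises at most about 1.2 PD of a 1 to 30 PD range.

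**4. Does the omission make the error larger or smaller?** Let s be the per-eye reading SD, ρ the between-eye error correlation, and k the SD of the between-eye kappa difference. The documents give none of these, so every value below is an assumption.

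Between-eye SD = √(2s²(1 − ρ) + k²)

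- s = 1.0 degree, ρ = 0, k = 0 / 0.5 / 1.0 / 1.5: 1.41 / 1.50 / 1.73 / 2.06 degrees, against a one-eye SD of 1.0 (kappa removed).
- Same inputs, but the one-eye value is taken as a difference from a single central image of that eye (SD √2 × 1.0 = 1.41): ratios 1.00 / 1.06 / 1.22 / 1.46.
- k = 0, ρ = 0.5: factor √(2 × 0.5) = 1.00. With ρ = 0.75: √(2 × 0.25) = 0.71.
- Kappa left in the one-eye angle, with s = 0.5, kappa SD 1.5 and between-eye kappa correlation 0.8: one eye √(0.25 + 2.25) = 1.58; between eyes √(0.5 + 2 × 2.25 × 0.2) = 1.18. With correlation 0.5 the between-eye value is √(0.5 + 2.25) = 1.66.

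The direction changes with the assumptions.

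**The case against.** **The between-eye output is tested elsewhere.** The SAP's Aim 2 regresses the app's strabismus angle on the cover test with prism neutralization (CTPN). The protocol's clinical study compares app phoria with the Modified Thorington (MT) test. Both carry the second eye's error and any kappa difference, and the hypothesis names clinical tests as an alternative reference. This stands. A reader might infer that the hypothesis is never tested on the app's own output, and the documents do not support that. The gap is confined to the ground-truth component. Even so, CTPN and MT have measurement error of their own and do not replace a geometrically known truth.

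**The setup is disclosed.** Aim 1 says openly that non-strabismic volunteers look off axis, the protocol notes that actual use will differ, and the SAP's slope and intercept are evidently calibration quantities. This also stands, and it makes the problem mainly one of what the result is called and what is claimed from it. The Hypotheses and Secondary outcome 1 nevertheless do make the claim.

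**The capture mode is unknown.** The protocol allows monocular or binocular measurement and does not say which was used for the ground-truth study. If only one eye was captured, the per-eye reading is confirmed, but no between-eye re-analysis is possible.

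**The ground-truth eligibility criteria also admit strabismus.** This does not help: target geometry fixes only the direction of the fixating eye, so the true between-eye deviation of such a participant would be unknown.

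**Conclusion.** The mismatch holds. Aim 1 yields per-eye gaze-angle accuracy within about ±23 PD. It does not yield ground-truth accuracy for strabismus, and it has no targets from 23 to 30 PD. It omits between-eye differences in kappa and HR on any reading. It omits the second eye's reading error unless the one-eye value is already a difference of two images.

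A reader might go further and infer that Aim 1 is an easier measurement, so that true strabismus error must be larger, for example by 50 to 73% (1.50 and 1.73 against 1.0). The documents do not support that. Those figures need an assumed per-eye SD of 1.0 degree, an assumed kappa-difference SD of 0.5 to 1.0 degree and zero between-eye correlation. Errors shared by both eyes cancel in a difference, a central-image reference already contains two readings, and kappa left in the one-eye angle can reverse the order. The SAP speaks of absolute angles and the protocol of angles relative to central fixation, so even the handling of kappa is unclear.

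The conclusion rests on the inference that the regression is per eye and, for the 0.7 degree bound, on an assumed IPD of 50 to 70 mm. The point should be corrected because it changes what Aim 1 can conclude. It does not invalidate the clinical comparisons.

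**What to change.** 1. Describe the Aim 1 result as per-eye gaze-angle calibration within about ±23 PD. Do not claim ground-truth accuracy for strabismus, or for 23 to 30 PD, from it.
2. State the capture mode. Where both eyes were imaged, also report the same-image right-minus-left app reading at each target against the geometric between-eye difference (at most about 0.7 degree). Give the mean difference and 95% limits of agreement, allowing for repeated targets within subject.
3. State whether kappa is removed before absolute gaze angles are compared with target angles.
4. Optionally, pair the right eye at one target with the left eye at another to simulate larger deviations, up to 26 degrees (100 × tan 26° = 48.8 PD). Label this as supplementary: it joins two photographs and two fixations, so it is not the app's single-picture output.

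**Cost.** A little extra analysis and an IPD for each subject, measured or assumed. Item 2 depends on both eyes having been captured and the images kept, which the documents do not confirm. The Aim 1 claim becomes narrower.
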